We will implement a traditional 3+3 (rule-based, modified Fibonacci) dose escalation design, with 3:1 randomization to active treatment vs sham control. There will be 6 dose tiers, reflecting increasing intensity and duration of stimulation: Tier 1 – 1 mA, single 20 - min cycle; Tier 2– 2 mA, single 20 min cycle; Tier 3 – 1 mA, 2 cycles of 20 min/20 min off; Tier 4– 2 mA, 2 cycles of 20 min/20 min off; Tier 5 – 1 mA, 3 cycles of 20 min/20 min off; Tier 6 – 2 mA, 3 cycles of 20 min/20 min off (Figure 7). Patients in the sham stimulation arm at all the tiers will have the cap and electrodes in place, and switches moved but without any delivered electrical stimulation. While the highest dose tier in this study is expected to be fully safe, based on preclinical and clinical studies^{12,19}, since this is a first-in-human study in acute stroke, a formal escalation to higher dose tiers is prudent.

Figure 7. This figure shows the 6 escalating tiers. Blue represents 1 mA and purple shows 2 mA of tDCS. Symptomatic ICH (SICH) in none of the three patients in a tier will result in escalation. However, SICH in one patient, 3 more patients and 1 sham will be enrolled at the same tier.

D.4. Management during and post stimulation period

Figure7: Technician-filled tolerability form	Presence		Severity		Effect on the study treatment (Shortened the stim duration)		Duration/Frequency			Treatment			
	A	P	M	Mod	S	Y	N	< 50 % of stim period	≥50% of stim period	lasted after stim period (min)	None	Con	Med
Adverse Events													
Rash													
Skin dryness													
Hair loss													
Itching													
Hives													
Skin Sensitivity to light													
Skin soreness													
Skin redness													
Skin darkening													
Numbness													
Tingling													
Dizziness													
General Pain													
Headache													

*A=Absent, Con=Conservative therapy such as cold pack and lotion, M= Mild, Mod=Moderate, Med=Medication such as topical steroid, N= No, P= Present, R: Resolved, S: Severe, Stim= Stimulation, Y=Yes.

Figure 8. Shows the technician-filled tolerability form. The selected items are based on the most common reported adverse effects associated with tDCS.

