After randomization and during the stimulation, all patients will be monitored closely by a physician-investigator. NIHSS will be obtained at the end of each 20-minute stimulation cycle and a visual inspection of the skin and rate degree of any potential erythema under the electrode will be performed. Then, a tolerability form will be completed based on validated cutaneous, neurological, and pain items of the PRO-CTAE (Patient-Reported Outcomes version of the Common Terminology Criteria for Adverse Events) (Figure 8).^{49,50}

After the stimulation, nursing neurologic assessments will be performed by Neurointensive Care Unit or Stroke Unit nurses with extensive experience in monitoring acute stroke patients. Specifically, patients will be monitored for any signs of neurological worsening and will be queried on development of new or worsening neurological symptoms including headache, dizziness, numbness, or weakness, etc. If any sign or symptom of neurological worsening is suspected, the patient will be immediately assessed by the on-call neurologist and an immediate brain imaging (CT or MRI) will be obtained. Neuro-checks will be performed at 1h and 2h after stimulation and then every 2 hours in patients requiring Neurointensive Care and every 4 hours in patients requiring Stroke Unit Care. Subsequent care will be continued in these settings, including medical management per national guidelines for acute ischemic stroke management issued by the American Stroke Association.⁵¹ Patients will not receive NSAIDs as concomitant therapy for the first 7 days after enrollment. All patients will undergo a multimodal MRI or CT including standard parenchymal images, non-invasive angiography, and perfusion studies and formal NIHSS assessment at 2-hour and 24-hour following the end of the stimulation tier as part of the study protocol.

D.6. Study Visits and Data Acquisition

D.6.1 Schedule of Events

	Baseline	End of each 20-min stimulation cycle			2-hr	24-hr	Day 4	Day 30	Day 90
		1	2	3					
Consent	✓								
History / Exam	✓								
Routine Labs	✓								
Vital Signs	✓	✓	✓	✓					
Patient tolerability form		✓	✓	✓					
Technician tolerability form/Skin Inspection*	✓	✓	✓	✓					
Multimodal MRI or CT	✓				✓	✓			
NIHSS	✓	✓	✓	✓	✓	✓			✓
Modified Rankin Scale (mRS)	✓						✓	✓	✓
Barthel Index (BI)									✓
EuroQol (EQ-5D)									✓
AMC Linear Disability Scale									✓
Interval serious adverse events		✓	✓	✓	✓	✓	✓	✓	✓

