The lead safety endpoint adverse event is symptomatic intracranial hemorrhage (SICH), defined using the SWIFT PRIME trial criteria⁵⁵: an increase of 4 or more points on the NIHSS within 24 hours of stimulation associated with parenchymal hematoma type 1 (PH1), parenchymal hematoma type 2 (PH2), remote intraparenchymal hemorrhage (RIH), subarachnoid hemorrhage (SAH), or intraventricular hemorrhage (IVH). In addition, all hemorrhages, both symptomatic and asymptomatic, will also be separately classified and analyzed by radiologic subtype, as hemorrhagic infarction type 1 (HI1), hemorrhagic infarction type 2 (HI2), PH1, PH2, RIH, SAH, or IVH.⁵⁵ A central neuroimaging core lab, blinded to treatment assignment, will review all brain MRI scans obtained at 24h and rate presence and type of radiologic hemorrhagic transformation. In addition, in patients who experienced worsening by 4 or more NIHSS points in the first 24 hours, they will review any and all additional brain MRI or CT scans obtained during the 24h time period,

SICH is the primary safety endpoint of the current trial, but trial results will be assessed on a variety of additional safety, feasibility, and tolerability results as well. It is anticipated that, after completion of the current trial, the judgement of whether to proceed directly to a pivotal trial, to proceed to a larger safety and preliminary efficacy trial, or to not proceed with further development, will rest on a considered and informed assessment of all outcome measures. It is important therefore to collect data on a wide range of safety

endpoints and a wide range of measures of functional outcome, as is planned in this proposal. In making the selection of a primary safety endpoint, an emphasis was placed on ensuring patient safety throughout the course of the trial by choosing an endpoint with uncontested clinical relevance (Symptomatic Intracranial Hemorrhage).

D.6.10.3 Additional Adverse Events with Specific Interrogation

In addition to general screening for all serious adverse events and focused elicitation of symptomatic intracranial hemorrhage events, the following events will be specifically interrogated for and recorded in the case report forms: skin redness, scalp rash, hair loss, seizure, headache, sensitivity to light, new ischemic stroke, deep venous thrombosis, pulmonary embolism, pneumonia, acute MI.

E. Safety Monitoring

E.1. Data and Safety Monitoring Plan

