The trial will be monitored by an Independent Data and Safety Monitoring Board (DSMB). [name] from department of neurorehabilitation will lead the DSMB. DSMB will assess for the causal relationship of the serious adverse event to the study treatment as definite, probable, possible, unlikely, or unrelated.

DSMB will meet at the completion of each dose tier, review all safety data, and determine whether the study will proceed to the next dose tier. DSMB deliberations will be guided by: 1) a formal stopping/escalation rule, based on the occurrence of the lead safety endpoint, symptomatic intracranial hemorrhage (SICH), and 2) The DSMB members' clinical judgement upon review of all other safety outcomes. In addition, DSMB will monitor separately the patients who enroll in the study with a stroke scale 0-3 during the study as they are treated to determine if they have an increase in NIHSS of 2 or more or which is disabling.

Furthermore, Food and Drug Administration (FDA) will be notified if there is one occurrence of SICH prior to repeating the tier or escalating to a higher tier.

E. 2. Statistical Design and Analyses Plan

E.2.1. Sample size

The study sample size derives from the use of the 3+3, rule-based, modified Fibonacci, dose escalation design, with 3:1 randomization to active treatment vs sham control. There will be 6 dose tiers, reflecting increasing intensity and duration of stimulation (Figure 7). The 3+3 study design (3 patients and 1 sham) with 6 dose tiers yields a sample size of at least 24 and potentially up to 48. The 3+3 design is the classical approach to dose escalation in first-in-human studies.^{57,58} While newer, adaptive designs for dose escalation trials have been developed, they are more complex and have limited advantages when major toxicities are not expected.⁵⁹ Therefore, the rule-based, 3+3 design remains the dominantly employed approach in current dose-escalation studies. We will take every step to avoid missing data by scheduling of the follow-up visits early in visit time windows and readiness to travel to the patient's location to perform needed assessments. Should any missing data occur, primary analyses will be performed using multiple imputation, with sensitivity analyses including complete case and worst possible outcome analyses.⁶⁰

E.2.2. Baseline characteristics

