The demographic and baseline clinical characteristics of the study population will be delineated with standard descriptive statistics. Categorical variables describing the clinical history, examination findings, and initial treatment will be summarized by

frequencies. Continuous variables such as vital signs, laboratory results, and time variables will be characterized by means, standard deviations, and 95% confidence intervals (CI). Ordinal and non-normally distributed variables (such as the NIHSS) will be characterized by medians and interquartile ranges. Baseline characteristics will be compared between the tDCS stimulation group with sham group to assess covariate balance. Wilcoxon Rank-Sum tests will be used for continuous or ordinal variables; Fisher's exact tests and chi-square tests will be used for grouped or nominal categorical variables.

E.2.3. Safety and Tolerability (Specific Aim 1)

E.2.3.1 Dose Escalation

The study Data and Safety Monitoring Board (DSMB) will meet at the completion of each dose tier, review all safety data, and determine whether the study will proceed to the next dose tier. DSMB deliberations will be guided by: 1) a formal stopping/escalation rule, based on the occurrence of the lead safety endpoint, symptomatic intracranial hemorrhage (SICH), and 2) The DSMB members' clinical judgement upon review of all other safety outcomes. The formal dose escalation rule uses SICH frequency to gate the occurrence and pace of escalation through the 6 dose tiers. If no SICH occurs in the 3 active patients at a dose tier, enrollment may escalate to the next dose tier. If one SICH occurs, 3 more active (and 1 more control) patient will be enrolled at that dose tier before escalation. If 2 SICHs occur at a dose tier, further study enrollment is held until detailed review by the DSMB (Fig 6). In addition, whenever the formal SICH criteria for dose escalation has been met, the DSMB will formally meet, review the SICH data and all other safety data, and advice regarding proceeding to the next tier, continuing at the current tier, or placing the study on hold.

E.2.3.2. Primary Safety Endpoint Analysis

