For the final statistical analysis of the primary SICH safety endpoint, a chi-square test will be used to detect differences in the rate of SICH between the active treatment and sham patients and higher and lower dose tiers. The treatment will be considered to have exhibited adequate safety in the current trial to proceed to future, larger, pivotal efficacy trials if tDCS results in lower or equivalent rates of SICH compared to sham.

E.2.3.3. Secondary Safety Endpoints Analysis

In secondary safety endpoint analyses, the following will be compared between the active treatment and sham patients, and between higher and lower dose tiers, using chi-squared tests: **1) Asymptomatic ICH by 24h** (intracranial hemorrhage not associated with NIHSS worsening ≥ 4); **2) Early neurologic deterioration** (worsening ≥ 4 on NIHSS during the 24-hour period after stimulation, with or without intracranial hemorrhage); **3) All-cause mortality at day 90 (mRS);** and **4) All serious adverse events.**

E.3.3. Tolerability Endpoint Analysis

The lead tolerability endpoint is completion of the protocol-assigned stimulation treatment without early cessation due to cutaneous, neurologic, nociceptive or other adverse effects. Experience with tDCS in post-stroke patients indicates only infrequent cutaneous (itching, tingling) adverse effects are likely to occur. Accordingly, for the current study, a patient will be considered to have tolerated the procedure if at least 75% of the stimulus period was completed. The treatment will be considered generally tolerable if, among all enrolled patients, tolerated procedures are achieved in $\geq 90\%$ of patients, assessed with a one-sided p value of 0.025. Secondary tolerability endpoints will be the

rate and severity of cutaneous, neurological, and pain items of the technician-filled (Figure 7) and patient-filled tolerability forms ⁴⁹, descriptively compared between active treatment and sham patients, and between higher and lower dose tiers.

E.3.4. Feasibility Endpoint Analysis (Specific Aim 2)

A time-motion analysis and mock run-throughs will be conducted prior to first enrollment. Nonetheless, it is anticipated that processes to optimize rapid placement of the cap and electrodes will continue to improve with experience gained from initially enrolled patients. The predefined success threshold for feasibility will be median time from randomization to tDCS initiation \leq 10 minutes in the last 10 enrolled patients.

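### The escalation rule in E.2.3.1 counts three active patients without asking how much stimulation they received, so a tier can be cleared on a lower tier's dose

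*Combined protocol and SAP*

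**What the plan says.** **Clearing a tier.** E.2.3.1: "If no SICH occurs in the 3 active patients at a dose tier, enrollment may escalate to the next dose tier". The Figure 7 legend in D.4 agrees: "Symptomatic ICH (SICH) in none of the three patients in a tier will result in escalation". After one event, "If one SICH occurs, 3 more active (and 1 more control) patient will be enrolled at that dose tier before escalation". None of these sentences mentions dose received, completeness of follow-up or replacement.

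**Completion.** The lead tolerability endpoint in E.3.3 is finishing the assigned stimulation "without early cessation due to cutaneous, neurologic, nociceptive or other adverse effects", and a patient counts as having tolerated it at 75% or more of the period. That threshold also appears in Hypothesis I-c. It is used only for tolerability. The technician form in D.4 has a column for whether an adverse event shortened stimulation.

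**The gating event.** D.6.10.2 defines SICH by "an increase of 4 or more points on the NIHSS within 24 hours of stimulation" together with a qualifying hemorrhage. Hypothesis I-a and the design overview before D2 place it in the 24-hour period after stimulation.

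**Assessment.** The section on management during and after stimulation requires multimodal imaging and "formal NIHSS assessment at 2-hour and 24-hour following the end of the stimulation tier as part of the study protocol". E.2.1 mentions visit time windows, but none is defined. Its missing-data provision (multiple imputation) is for the primary analyses, not the tier decision.

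**Oversight.** Under E.1 and E.2.3.1 the DSMB meets at the end of each tier, reviews all safety data and may advise proceeding, continuing at the tier or holding.

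**The concern.** In a 3+3 design the evidence that a tier is safe is the zero in 0/3. That zero is informative only if the three patients were exposed to the tier's dose. The plan has a completion standard and a form that records shortened sessions, but the escalation count uses neither.

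The tier structure makes this concrete. Tiers 3 to 6 add cycles at the same two current levels, so a session cut short between cycles reproduces a tier already passed. An event-free patient of that kind repeats the lower tier's evidence and is credited to the higher one. The next cohort is then exposed on fewer relevant observations than the rule appears to require. D.4 justifies formal escalation on the ground that this is the first human study in acute stroke, and the trial is meant to identify regimens for later trials. Both purposes depend on each tier having been tested at its own dose.

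**Working it through.** **1. The plan's own figure.** According to E.2.1 the design "yields a sample size of at least 24 and potentially up to 48". Check, with six tiers and cohorts of three active patients plus one sham: 6 × (3 + 1) = 24, and with every tier expanded once 6 × 2 × (3 + 1) = 48. Both reproduce. The count has no allowance for replacements.

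**2. What a shortened session delivers.** Inputs are the D.4 tiers (1 mA for tiers 1, 3 and 5; 2 mA for tiers 2, 4 and 6; one, two or three 20-minute cycles). Percentages are of current-on time.

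| Assigned tier | Stops after | Share delivered | Equals |
|---|---|---|---|
| 3 | cycle 1 of 2 | 20/40 = 50% | tier 1 |
| 4 | cycle 1 of 2 | 20/40 = 50% | tier 2 |
| 5 | cycle 1 of 3 | 20/60 = 33% | tier 1 |
| 5 | cycle 2 of 3 | 40/60 = 67% | tier 3 |
| 6 | cycle 1 of 3 | 20/60 = 33% | tier 2 |
| 6 | cycle 2 of 3 | 40/60 = 67% | tier 4 |

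Every row is below the 75% in E.3.3.

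**3. Conditional effect on the gate.** Let p be the true SICH probability at the full assigned dose and m the number of the three active patients who received it. Assume an under-dosed patient has zero SICH risk. The documents give no value for p, so a range is shown. Chance that the first cohort clears = (1 − p)^m.

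| p | m = 3 | m = 2 | m = 1 |
|---|---|---|---|
| 0.10 | 0.729 | 0.810 | 0.900 |
| 0.20 | 0.512 | 0.640 | 0.800 |
| 0.30 | 0.343 | 0.490 | 0.700 |
| 0.50 | 0.125 | 0.250 | 0.500 |

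The one-sided 95% upper bound after zero events is 1 − 0.05^(1/m): 63% for 0/3, 78% for 0/2 and 95% for 0/1.

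**4. Averaged effect.** Let q be the chance that an active patient stops early, independently of the others. The documents do not give q; 5% and 10% are assumed. A 3-patient cohort contains at least one early stopper with probability 1 − (1 − q)^3: 1 − 0.95^3 = 14% and 1 − 0.90^3 = 27%. Averaged clearance is (1 − p(1 − q))^3.

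| p | q = 0 | q = 5% | q = 10% |
|---|---|---|---|
| 0.10 | 0.729 | 0.741 | 0.754 |
| 0.20 | 0.512 | 0.531 | 0.551 |
| 0.30 | 0.343 | 0.366 | 0.389 |
| 0.50 | 0.125 | 0.145 | 0.166 |

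At p = 0.30 the rise is about 2 to 5 percentage points.

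**5. The window.** The SICH window is 24 hours after stimulation. The formal NIHSS and scan are due 24 hours after the end of stimulation. The visit therefore sits on the closing edge, and with no tolerance stated, a visit a few minutes late falls outside.

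**The case against.** The best case for the plan has five parts.

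- **The rule does not act alone.** Its wording permits escalation and does not require it. The DSMB must meet first, sees all safety data and can advise continuing at the tier, which is a route to adding patients when exposure was poor. This stands as mitigation. But the board is guided by a formal rule that is silent on exposure, so two similar cohorts could be handled differently.
- **The documents never say that early stoppers count.** True. It follows from an unqualified count and the absence of any evaluability or replacement rule.
- **Early stopping may be rare.** E.3.3 anticipates only infrequent cutaneous effects. A reader might take 10% as the plan's forecast. It is an acceptance limit over all enrolled patients, sham included. Nor do the documents say that intolerance rises with tier.
- **Bleeds would be seen anyway.** A reader might infer that a late or missed 24-hour visit hides a SICH. The documents do not support that as likely: neuro-checks run at 1 and 2 hours and then every 2 or 4 hours, suspected worsening triggers immediate imaging, and the core lab reviews extra scans in patients who worsen by 4 or more points. None of this addresses under-dosing.
- **The window is counted from the end of stimulation.** Counting from the start would put the 24-hour visit 20 to 100 minutes outside. Hypothesis I-a and the design overview refer to the period after stimulation, so that reading falls. Only the edge problem remains.

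**Conclusion.** The concern holds for delivered exposure. Followed literally, E.2.3.1 and the Figure 7 legend credit a higher tier with event-free patients who received a lower tier's dose, and nothing in the plan corrects this except DSMB judgement. It should be fixed, but it is not a finding that the trial would escalate unsafely.

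The size depends on assumptions the documents do not supply. When a cohort does contain one or two under-dosed patients, the loss is large: at an assumed 30% SICH rate, first-cohort clearance goes from 34% to 49% or 70%. A reader might take those as the overall effect of the gap. They are conditional on early stopping having happened; averaged over 5% to 10% early stopping, clearance is about 37% to 39%. All figures come before DSMB review, concern the first cohort only, and use zero SICH risk after under-dosing, which overstates the effect if partial exposure carries some risk.

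The missing visit tolerance at 24 hours is a real but secondary defect of wording.

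**What to change.** Reconcile E.2.3.1 and the Figure 7 legend with E.3.3, D.6.10.2 and the visit schedule, so that together they state:

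- the number needed to clear a tier is made up only of active patients who meet a pre-stated exposure standard and have the 24-hour NIHSS and imaging;
- any SICH counts against the tier, whatever the exposure;
- an active patient who does not count is replaced at the same tier, stays in all safety and tolerability analyses, and is reported to the DSMB with the stimulation delivered;
- the scheduled 24-hour assessment lies inside the SICH window, with a visit tolerance given.

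The exposure threshold and the tolerance are for the sponsor and DSMB to set. The plan's own 75% is an available reference, but it was written for tolerability. The text should also say how replacement works within the 3:1 randomization.

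The cost is a few sentences, a slower pace and a few more patients. With 18 active patients (6 × 3), 5% to 10% early stopping implies 0.9 to 1.8 replacements; with 36 (every tier expanded), 1.8 to 3.6. Patients lacking a 24-hour assessment would add to this. Since replacements raise the minimum above 24, and could take the total past 48 if every tier expands, the sample size in E.2.1 and D3 should be restated.

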As indicated in the PI Assurances as part of the IRB requirements for approval, the PI has ultimate responsibility for the conduct of the study, the ethical performance of the project, the protection of the rights and welfare of human subjects, and strict adherence to any stipulations imposed by the IRB.

The PI and study team will comply with all UCLA policies and procedures, as well as with all applicable Federal, State, and local laws regarding the protection of human subjects in research, including, but not limited to, the following:

- Ensuring that the personnel performing the project are qualified, appropriately trained, and will adhere to the provisions of the approved protocol,
- Implementing no changes in the approved protocol or consent process or documents without prior IRB approval (except in an emergency, if necessary to safeguard the well-being of human subjects and then notifying the IRB as soon as possible afterwards),
- Obtaining the legally effective informed consent from human subjects of their legally responsible representative, and using only the currently approved consent process and stamped consent documents, as appropriate, with human subjects,
- Reporting serious or unexpected adverse events as well as protocol violations or other incidents related to the protocol to the IRB according to the OHRPP reporting requirements.
- Assuring that adequate resources to protect research participants (i.e., personnel, funding, time, equipment and space) are in place before implementing the research project, and that the research will stop if adequate resources become unavailable.
- Arranging for a co-investigator to assume direct responsibility of the study if the PI will be unavailable to direct this research personally, for example, when on sabbatical leave or vacation or other absences. Either this person is named as co-investigator in this application, or advising IRB via webIRB in advance of such arrangements.

Investigational Plan:

Protocol: Transcranial electrical Stimulation in Stroke EaRly After onset Clinical Trial (TESSERACT)

Overview of Protocol of TESSERACT

Title	Transcranial electrical Stimulation in Stroke EaRly After onset Clinical Trial (TESSERACT)
Objective	To evaluate the safety, tolerability, and feasibility, and preliminarily explore the potential efficacy, of transcranial direct current stimulation (tDCS) as an innovative non-invasive neuroprotection technique in acute ischemic stroke.

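### Within a dose tier, a single stimulation-related SAE or a first SICH does not pause enrolment, so up to 2 more active patients can be treated before the tier-end review

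*Combined protocol and SAP*

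**What the plan says.** The rule is in E.2.3.1 (Dose Escalation) and E.1 (Data and Safety Monitoring Plan) of the combined protocol and SAP.

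- **No SICH in the 3 active patients of a tier:** enrolment may move up.
- **One SICH:** "If one SICH occurs, 3 more active (and 1 more control) patient will be enrolled at that dose tier before escalation". No pause is attached. E.1 adds that the FDA "will be notified if there is one occurrence of SICH prior to repeating the tier or escalating to a higher tier".
- **Two SICHs:** "If 2 SICHs occur at a dose tier, further study enrollment is held until detailed review by the DSMB". This is the only enrolment hold with a written trigger.
- **Scheduled board review:** "DSMB will meet at the completion of each dose tier, review all safety data". The board can weigh every other safety outcome by clinical judgement at that point.
- **Further board meeting:** "whenever the formal SICH criteria for dose escalation has been met, the DSMB will formally meet", with advice to move up, stay at the tier or put the study on hold.

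Other provisions do operate while a tier is running. E.1 states that "DSMB will assess for the causal relationship of the serious adverse event to the study treatment as definite, probable, possible, unlikely, or unrelated", and that "DSMB will monitor separately the patients who enroll in the study with a stroke scale 0-3 during the study as they are treated". The PI assurances at the front include "Reporting serious or unexpected adverse events as well as protocol violations or other incidents related to the protocol to the IRB" and allow emergency protocol changes to protect subjects. The section on management during and after stimulation provides physician monitoring, and immediate neurologist assessment with imaging if worsening is suspected.

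**The concern.** The protocol describes itself as the first use of this treatment in humans with acute stroke, and it gives possible blood-brain-barrier effects as a reason for escalating by dose (C.3). It specifically asks about seizure and new ischemic stroke (D.6.10.3). Its secondary safety endpoints include early deterioration with or without hemorrhage, 90-day mortality and all SAEs (E.2.3.3). So harms other than SICH are recognized, yet none of them is tied to enrolment inside a tier.

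Suppose the first active patient in a tier has a seizure that the DSMB grades as probably caused by stimulation. A team following the plan exactly may randomize the next patient to the same dose, and the one after that, before the board is required to consider whether to continue. The same is true after a first SICH, whose written consequence is a larger tier and not a pause. The board and the causality scale already exist. What is missing is a link from the grade to the next randomization.

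**Working it through.** **Inputs from the documents.** Six tiers, each with 3 active and 1 sham patient, expandable once by the same number (E.2.1, E.2.3.1); 8-16 enrolments a year (D3 Subjects).

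**The plan's own figure.** Minimum N = 6 × (3 + 1) = 24. Maximum N = 6 × (6 + 2) = 48. Both match E.2.1. With no expansion there are 6 × 3 = 18 active patients.

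**Does any within-tier provision require a pause?**
- Causality grading: no timeline and no consequence for enrolment.
- Monitoring of patients enrolled with NIHSS 0-3: one subgroup, no hold attached.
- FDA notice: due before the tier is repeated or escalated, so it acts between cohorts.
- IRB reporting and emergency changes: a duty to report and a permission to act.
- Bedside monitoring and imaging: protects the affected patient, not the next one.

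None does.

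**Bound.** If the event is in active patient *k* of 3, then 3 − *k* active patients remain: 2, 1 or 0.

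**Expected further exposures per standard tier.** The documents give no related-SAE rate in acute stroke, so *p* per active patient is assumed.

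E = 2p + 1·p(1 − p) + 0 = 3p − p²

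- p = 1%: 0.03 − 0.0001 = 0.0299
- p = 5%: 0.15 − 0.0025 = 0.1475
- p = 10%: 0.30 − 0.01 = 0.29

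If every event were a SICH, the two-SICH hold would trim this to 3p − 2p² (0.28 at 10%).

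**From exposures to events.** Multiplying by *p* and by six tiers gives a ceiling on further events over the trial:
- 1%: 6 × 0.0299 × 0.01 = 0.002
- 5%: 6 × 0.1475 × 0.05 = 0.04
- 10%: 6 × 0.29 × 0.10 = 0.17

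These are ceilings because they assume no tier-end hold, every event known in time, and every review ending dosing.

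**Would a review arrive in time?** Mean spacing between patients is 365/16 ≈ 23 to 365/8 ≈ 46 days. Assume random arrivals at rate *r* a year and 3 days for grading. The chance that the next patient is randomized first is 1 − exp(−r·d/365), for r = 8 to 16:
- Event on day 1 (d = 4): 8% to 16%
- Event on day 30 (d = 33): 51% to 76%
- Event on day 90 (d = 93): 87% to 98%

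**The case against.** The strongest reply is that finishing a cohort of three before deciding is the classical 3+3 approach, which E.2.1 adopts openly. The DSMB sees all safety data at tier end and can hold the study. Causality grading is not confined to tier-end meetings. Patients arrive weeks apart at one site under close physician observation. Earlier experience is also reassuring: the protocol reports no SAEs with tDCS in other settings (section B) and places every tier within ranges safe in other patients (C.3). All of this stands as a reason to expect small numbers. It does not supply the missing instruction, because none of these provisions obliges anyone to stop before the next randomization.

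A second reply is that a first SICH is already partly handled, and this also stands. A reader might infer that in a tier expanded to 6 active patients, 5 could be treated after an event in the first. The documents do not support that. The FDA must be told before a tier is repeated, and the board's advice includes staying at the current tier. The natural reading puts both between the first cohort and the second, so the exposure is limited to the rest of the current cohort.

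Third, deaths and ischemic worsening are also natural outcomes of an occlusive stroke and may well be graded only possible. A pause limited to definite or probable would then miss them. That is a real limit of the remedy, accepted so that expected stroke complications do not repeatedly stop enrolment.

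**Conclusion.** The point holds for the remainder of the current cohort. The only written enrolment hold within a tier is two SICHs. After one related SAE or a first SICH, at most 2 more active patients can receive the same dose before the tier-end review. The bound needs no assumption about rates. The expected numbers (0.03, 0.15 and 0.29 exposures per standard tier) do: they rest on assumed rates of 1%, 5% and 10%, and the true rate may be low.

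A reader might go further and conclude that non-bleeding events escape oversight, or that the plan exposes patients to a known excess of harm. Neither follows. The board reviews all safety data at each tier end and may hold the study on clinical judgement, and the figures count patients treated, not patients injured.

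This is a cheap improvement and not a flaw that undermines the design. The conclusion rests on the text; the figure cited for the rule in E.2.3.1 could not be read, although the Figure 7 caption repeats the SICH-based rule for escalation and expansion.

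**What to change.** In E.1 and E.2.3.1, add two statements:

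- (a) Every SAE in a treated patient is sent promptly to the DSMB for causality grading.
- (b) Randomization pauses when an SAE is graded definite or probable. It also pauses immediately on recognition of a first SICH in an active patient, without waiting for grading. In both cases it stays paused until the DSMB advises to continue, stay at the tier or hold.

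Part (b) changes the present handling of a first SICH, which now leads to expansion with no pause. SICH remains the sole 3+3 count. The two-SICH hold, the tier-end meetings and the NIHSS 0-3 monitoring stay as written, and N stays 24-48.

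The cost is protocol wording, occasional unscheduled DSMB calls and short pauses. With 18 active patients and an assumed 5% rate, 18 × 0.05 = 0.9 pauses are expected. At 7 days each, missed patients number 0.9 × 8 × 7/365 = 0.14 to 0.9 × 16 × 7/365 = 0.28, or about 0.1-0.3 over the trial. Scaling this to 36 active patients would be wrong at such rates, because 36 requires all six tiers to expand and so at least six SICHs.

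The gain is mainly for events in the first days. It is small for events recognized between day 30 and day 90, when the next patient has usually been randomized already.
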